9 QUALITY CONTROL AND DATA MONITORING PROCEDURES

We will review study progress, and data and safety issues on a regular basis in the following ways:

8.1. Training

All study staff will complete PEERRS Human Subjects Research Protection course and Good Clinical Practice for Social and Behavioral Research training. They will also be trained on the project protocol, project data collection systems and other study-related topics by the Principal Investigator and/or Project Manager and Project Coordinator prior to beginning data collection. Additionally, the Project Coordinator will develop a detailed manual of procedures, which will provide step-by-step instructions on the conduct of the trial. The manual of procedures and other study documents will be reviewed in detail with the staff and student research assistants involved in data collection. Additionally, any staff who join the team after the project starts will be required to complete the standardized training prior to enrolling participants. Training will be documented in an electronic regulatory binder.

8.2. Meetings

- *Study staff meetings*: Drs. [name], the Project Manager, and the Project Coordinator will meet weekly throughout the course of the project to ensure that all data quality and IRB policies and procedures are being followed. This will include reviewing recruitment challenges, and monitoring data collection and quality.
- *Quarterly meetings with Cornell Roybal Executive Committee*: [name] will meet quarterly with the Directors and Executive Committee of the Cornell Roybal Center to report on study progress. These meetings will be either in Executive Committee sessions or in the Work-in-Progress seminar. She will also

meet as needed with Cornell's Roybal Center Director [name] and Co-Director [name] to provide updates and discuss any problems with implementation of this pilot study.

- *Meetings with Western Wayne Family Health Centers:* [name] and [name] and/or other staff members will meet at least monthly with [name], Special Projects Manager at Western Wayne Family Health Centers, and/or other administrators as well as the Community Health Worker, when hired. During the active intervention period, the Project Manager, [name], or other designated staff member, will meet with the Community Health Worker weekly, to provide feedback to ensure optimal fidelity to protocols and to problem-solve as needed. [name] or another WWFHC representative will be invited to attend these meetings as well.

8.3. Auditing

- Conformance with Informed Consent Requirements. At approximately the study's midpoint and end, the project manager and/or PI will also review all consent forms for participants.
- Quality Control for Telephone Interviews: We will check a random 10% of all data from telephone interviews input into REDCap by listening to audiorecordings of the interviews and verifying that data was input correctly. Any deviations will be discussed at regular study staff meetings.

To document adherence to this plan we will maintain a monitoring log and create accompanying monitoring reports for each review. The monitoring log will be kept in the electronic regulatory binder.

8.4 Protocol Deviations

This protocol uses the University of Michigan definition of a protocol deviation (<https://az.research.umich.edu/medschool/glossary/deviation>) which defines a protocol deviation as “an incident involving non-compliance with the protocol, but one that does not have a significant effect on the subject’s rights, safety or welfare, and/or on the integrity of the data. Deviations may result from the action of the participant, researcher or staff.”

Reportable protocol deviations will be reported and tracked in the REDCap database and will be discussed at investigator and project staff meetings.

The following events will not be reported as protocol deviations:

- A protocol deviation will not be reported for participants who skip/do not complete telephone interview items or entire interviews. Participants can decline to answer any survey question for any reason. We expect in an intensive, long duration protocol like this that participants may miss some assessments.
- A protocol deviation will not be reported for out-of-window assessments. Use of this data will be assessed by the study investigators for each study analysis; some analyses may need tighter compliance to the assessment window while others will not.
- A protocol deviation will not be reported if an intervention group participant completes their 8-week survey before they have completed the final intervention session.
- A protocol deviation will not be reported if a participant misses an intervention session.

Reportable protocol deviations will be reviewed at the project staff and investigator meetings and submitted to the U-M IRB--HSBS and in other DSMB or NIH reports (if applicable).

10 CONFIDENTIALITY AND PRIVACY

Overview

A number of steps will be taken to ensure participant confidentiality and to protect against the potential risks related to stress from loss of confidentiality, or potential coercion. Participants will be encouraged to ask questions throughout recruitment/screening calls and informed that their participation is voluntary and that they can refuse to participate at any time without penalty. Participants also will be reminded that they can skip questions in surveys that they may not wish to answer. As part of their consent process, participants will be informed about the small risk of a breach of confidentiality. All data collection will take place over the telephone, such that participants can choose a location with the level of privacy they desire. There will be a line in both the recruitment/screening script and the telephone survey script, “Are you in a comfortable place that has the privacy that you desire?” If the answer is no, we can reschedule the interview.

Email and text messages will only be used to reply to or contact participants if they choose this mode. A secure UM email (Google) account will be used for the study and will be monitored by study staff. Throughout the study, IRB guidelines will be followed to ensure the privacy and integrity of the information we collect. Any breach of confidentiality will be immediately reported to the PI and to the University of Michigan Health Sciences and Behavioral Sciences IRB, as an ORIO. In addition, any complaints or concerns expressed to the study staff by participant participants, providers, or anyone else affected by this study will be immediately reported to the PI, and to the IRB as an ORIO. All research data will be presented in reports, presentations, or manuscripts in aggregate statistics only.

Training and Monitoring

As noted above, all study staff, including community health workers, and research assistants will complete the web-based University of Michigan's PEERRS (Program for Education and Evaluation in Responsible Research and Scholarship) course in Human Subjects Research Protection and NIH-approved Good Clinical Practice Training (NCATS Social and Behavioral Best Practices). Proof of their certification and completion of the training programs will be kept on file. Staff will have signed a pledge of confidentiality, and we will ensure that all staff understand that a breach of confidentiality is grounds for dismissal. Training of staff will include information about the importance of privacy and confidentiality and specific techniques to maintain confidentiality of all information in the context of this study. Regular study team meetings will be used to ensure that all data quality protocols and IRB policies and procedures are being followed.

Managing and Protecting Data

All study participant information will be collected, stored and managed by trained study staff and research assistants in REDCap. REDCap is a secure, web-based application designed to support data capture for research studies, providing 1) an intuitive interface for validated data entry; 2) audit trails for tracking data manipulation and export procedures; 3) automated export procedures for seamless data downloads to common statistical packages; and 4) procedures for importing data from external sources. It is HIPAA compliant and supported by the University of Michigan. This secure web application promotes high quality data collection; forced responses ensure that interviewers are not able to proceed with the survey if required data are missing; and each survey is designed so that only valid responses are entered.

UM Qualtrics will be used to collect contact information for individuals interested in the study if they use the QR code available on the study flyer. UM Qualtrics is HIPAA compliant and secure. Qualtrics is a secure U-M

contracted-for cloud service that can be used to maintain or share the university's sensitive unregulated data, as well as some kinds of sensitive regulated data. Only UM study team members will be able to access this data and manually transfer it to the study's REDCap database for future contacts with potential participants. No other data will be collected or stored using UM Qualtrics.

For telephone calls and telephone-based intervention sessions, we will use Zoom Phone to audio record calls and CHW sessions for quality assurance. Zoom and Zoom Phone are HIPAA-compliant and supported by the University of Michigan. Audio recordings will be stored in the secure University of Michigan School of Public Health server or Dropbox at U-M, a HIPAA-compliant file storage system.

On-site Access and Control: Users are instructed to lock their workstation and to never leave it unattended with an active desktop. This enables access control by allowing only the credentials of the validated user to unlock the workstation. This is especially true when a user is accessing study data.

Remote Access: All connections from remote locations must use the University-configured Cisco VPN client, which encrypts all traffic to and from the servers.

All databases will be maintained in access-restricted files throughout the study. Study personnel who leave the research team will have their access to study files revoked.

The only paper records with identifiers will be the informed consent documents, and these will be kept in a locked office, in locked file cabinets in the University of Michigan School of Public Health. Access to the file cabinets will be restricted.

We will report AEs/SAEs to the IRB, DSMB or ISM, and/or other parties in a blinded manner, using only the unique subject identifier to protect the participant's identity.

Certificate of Confidentiality

To further protect the privacy of study participants, a Certificate of Confidentiality will be issued by the National Institutes of Health (NIH). This certificate protects identifiable research information from forced disclosure. It allows the investigator and others who have access to research records to refuse to disclose identifying information on research participation in any civil, criminal, administrative, legislative, or other proceeding, whether at the federal, state, or local level. By protecting researchers and institutions from being compelled to disclose information that would identify research participants, Certificates of Confidentiality help achieve the research objectives and promote participation in studies by helping assure confidentiality and privacy to participants.

11 STATISTICAL CONSIDERATIONS

11.1 Sample Size

This pilot study is not powered to determine the statistical significance of effects.

11.2 Data Analyses

11.2.1 General Approach

We will collect outcome data at two time points: baseline and 8 weeks from baseline (post-program, for those in the intervention group). All quantitative process and outcome data will be collected in REDCap. Descriptive statistics will be used to summarize background variables for the overall sample and by treatment group. Prior

to conducting primary analyses, descriptive analyses will be conducted to examine data distribution, outliers and potentially important covariates for inclusion in multivariate model diagnostics. We will evaluate normality using normal quantile plots and standard tests of normality incorporated in basic statistical packages, including SPSS and SAS.

11.2.2 Primary & Secondary Endpoints

We will calculate baseline descriptive statistics and compare groups using independent-sample t-tests for continuous variables and chi-squared tests for categorical variables. We will assess psychometrics of scales used (e.g., internal consistency reliability and concurrent validity). We will convert the PROMIS 6-item Pain Interference subscale score to T-scores (a standardized score with a mean of 50 and SD of 10) by summing the scales and using the conversion tables provided at HealthMeasures.net.

To assess the effect of being in the intervention group, we will use a univariate analysis of variance model for continuous primary and secondary outcomes. The dependent variable in each model will be the value of the outcome at 8-week follow-up; the independent factor will be treatment group (intervention vs. control), with the baseline value of the outcome as a covariate.

Effect size will be indicated by partial eta squared for the treatment group variable. In order to assess the potential clinical relevance of the intervention, we will use chi-squared tests to compare the percentage of participants in each treatment condition who achieved the Minimally Important Difference (MID) of ≥ 3 T-score points in PROMIS pain interference.

We will repeat this analysis with the secondary outcomes: Global Impression of Change in Pain and Functioning. Transformations for non-normality of outcomes will be performed as indicated.

We will also assess the moderating effect of selected variables such as sex, age, baseline pain intensity, and degree of program engagement. Moderation analyses will use standard approaches to evaluate interactions between these covariates and treatment group.

For patient engagement, the secondary outcome indicating feasibility that is composed of: 1) number of sessions completed out of 7; and 2) participant satisfaction on a 5-point Likert scale, we will calculate descriptive statistics. We will also explore differences by age group (under 65/65+) as well as gender. As an exploratory analysis, we will investigate whether satisfaction differs according to whether or not participants achieved the MID on the primary outcome of pain interference.

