11.2.1	General Approach	28
11.2.2	Primary & Secondary Endpoints	29
11.2.3	Other Pre-specified Analyses	29
12	Interim Analysis	30
13	Publications	30
14	protocol amendment history	30

STATEMENT OF COMPLIANCE

The trial will be carried out in accordance with International Conference on Harmonisation Good Clinical Practice (ICH GCP) and the following:

- United States (US) Code of Federal Regulations (CFR) applicable to clinical studies (45 CFR Part 46, 21 CFR Part 50, 21 CFR Part 56, 21 CFR Part 312, and/or 21 CFR Part 812)

National Institutes of Health (NIH)-funded investigators and clinical trial site staff who are responsible for the conduct, management, or oversight of NIH-funded clinical trials have

completed Human Subjects Protection and ICH GCP Training.

The protocol, informed consent form(s), recruitment materials, and all participant materials will be submitted to the Institutional Review Board (IRB) for review and approval. Approval of both the protocol and the consent form must be obtained before any participant is enrolled. Any amendment to the protocol will require review and approval by the IRB before the changes are implemented to the study. In addition, all changes to the consent form will be IRB-approved; a determination will be made regarding whether a new consent needs to be obtained from participants who provided consent, using a previously approved consent form.

PROTOCOL SUMMARY^{CT.GOV}

Title:

A pilot and feasibility study of a chronic pain self-management intervention for older adults incorporating podcasts and patient priorities.

Study Description:

This randomized pilot trial tests the feasibility of a community health worker (CHW)-delivered chronic pain self-management intervention for older adults ("STEP-UP"; Support, Training, and Education for Pain Self-Management – Using Podcasts) in a primary care setting.

Objectives*:

We will conduct a randomized (waitlist) pilot trial (n=40) in a Federally Qualified Health Center.

Endpoints*:

Primary Endpoint: Improvement in pain interference at 8 weeks (post-program)
Secondary Endpoints: physical functioning and global impression of change, and participant engagement and satisfaction (secondary outcomes) at 8 weeks

Study Population:

We will recruit 40 adults from a FQHC who are age 50+ with high-impact chronic pain.

Phase* or Stage:

Stage 1 (Behavioral Stage Model) Pilot Trial

**Description of Sites/Facilities
Enrolling Participants:**

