2 OBJECTIVES & ENDPOINTS

OBJECTIVES	ENDPOINTS	JUSTIFICATION FOR ENDPOINTS
Primary		
To determine if participating in the STEP-UP intervention leads to decreased pain interference with daily functioning.	PROMIS Pain Interference 6a scale is the primary endpoint (pain interference is assessed at baseline, and 8 weeks from baseline). A 2.5 point difference in T-score is considered clinically significant.	Pain interference is a patient-centered outcome that indicates pain's impact on valued and necessary activities. This intervention teaches skills such as goal setting to gradually increase engagement in daily activities.
Secondary		
To determine if participating in the STEP-UP intervention leads to greater improvement in Global Impression of Change in Pain and Functioning.	Patient Global Perception of Change since baseline will be assessed at 8 weeks. Participants will be asked about pain and functioning in separate items.	“Global impression of change” variables capture participants’ subjective perceptions of intervention benefit.

To assess participant engagement in the intervention.	Number of sessions (out of 7) completed at 8 weeks from baseline.	Given the novel nature of this intervention and the barriers that many participants may experience to engagement, it is important to assess whether the intervention as designed yields acceptable engagement levels.
To assess participant satisfaction with the intervention.	Items ask about overall satisfaction with the program, e.g., whether participation increased understanding of pain management (1= Strongly Disagree to 5= Strongly Agree). A higher score indicates higher patient satisfaction.	These items will facilitate understanding of the intervention's acceptability in the priority population as well as highlight potential areas for improvement prior to a larger trial or another future iteration of the intervention.

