3 STUDY DESIGN

3.1 Study Design

- NIH Behavioral Intervention Stage 1 randomized pilot trial to examine the acceptability and preliminary effects of the STEP-UP program on pain interference among older adults with chronic pain compared to a control group.
- Participants will be allocated into the two study arms in a 1:1 ratio by block randomization with mixed block sizes.

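### Partial eta squared is the only effect size named for the primary model: report the adjusted T-score difference with its 95% CI, and reconcile the 2.5-point and 3-point thresholds

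*Combined protocol and SAP*

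**What the plan says.** The primary endpoint is PROMIS Pain Interference 6a at 8 weeks, and the objective in Section 2 is directional: a reduction in interference. Section 11.2.2 introduces the model as follows: "To assess the effect of being in the intervention group, we will use a univariate analysis of variance model for continuous primary and secondary outcomes". Its response is the 8-week value, with the baseline value as a covariate, so this is an ANCOVA. For its result the section says: "Effect size will be indicated by partial eta squared for the treatment group variable". No other effect size is named for the model, and no section mentions an adjusted mean difference, a confidence interval or a confidence level. The descriptive summaries by arm in Section 11.2.1 concern background variables.

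Two thresholds appear for the same scale. The endpoint table in Section 2 says: "A 2.5 point difference in T-score is considered clinically significant". Section 11.2.2 plans a chi-squared comparison of the "percentage of participants in each treatment condition who achieved the Minimally Important Difference (MID) of ≥ 3 T-score points in PROMIS pain interference". It uses the same MID again in an exploratory analysis of "whether satisfaction differs according to whether or not participants achieved the MID on the primary outcome of pain interference". No planned analysis uses 2.5.

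On sample size, Section 11.1 says: "This pilot study is not powered to determine the statistical significance of effects".

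**The concern.** Once significance testing is set aside, what the primary comparison can offer is an estimate of the effect and a statement of its precision. Partial eta squared gives neither in usable form. It is the treatment sum of squares as a share of treatment plus residual. It takes the same value whichever arm did better, it changes with the residual SD, and it is biased upward in small samples. A reader given that figure alone could not say whether the intervention arm improved more, or whether a benefit of 2.5 or 3 points is compatible with the data. A team planning the next trial could not recover the T-score difference from it without also knowing the residual SD.

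The thresholds are a smaller issue. Section 2 does not say whether 2.5 is a difference between groups or a change within a person, whereas Section 11.2.2 plainly uses 3 as a person-level cut-off. The pair may be deliberate, but while it is unlabelled the benchmark could be chosen after the results are known.

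**Working it through.** The plan contains no power or precision figure to reproduce, so the check is illustrative.

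**Inputs from the documents**
- Total sample 40 (Protocol Summary) and 1:1 allocation (Section 3.1), so 20 per arm.
- ANCOVA on the 8-week value with baseline as covariate (Section 11.2.2), so residual df = 40 − 3 = 37.
- Thresholds of 2.5 points (Section 2) and 3 points (Section 11.2.2).
- T-score metric SD of 10 (Section 11.2.2). This belongs to the scale and is not an estimate for this population.

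**Assumptions (not in the documents)**
- Outcome SD 5 to 10.
- Baseline to follow-up correlation r from 0 to 0.7.
- 40 analysed, or 32 to allow for loss.
- Two-sided 95% confidence.

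**Residual SD and standard error**
- s = SD × √(1 − r²). The smallest value is 5 × √(1 − 0.49) = 3.57 and the largest is 10.
- SE = s × √(4/40) = 0.316 × s, which is 1.13 to 3.16 points.

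**From a T-score difference to partial eta squared:** t = difference / SE, and partial eta squared = t² / (t² + 37).

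| Difference | s = 10 | s = 3.57 |
|---|---|---|
| 2.5 points | t = 0.79, value 0.017 | t = 2.21, value 0.117 |
| 3 points | t = 0.95, value 0.024 | t = 2.66, value 0.160 |

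The two ranges overlap almost entirely, so the statistic cannot separate the two thresholds.

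**From partial eta squared back to points:** for a reported 0.05, t² = (0.05/0.95) × 37 = 1.947, so |t| = 1.395. Then |difference| = 1.395 × 0.316 × s = 0.441 × s, which is 1.58 to 4.41 points with the sign unknown. That range lies on both sides of 2.5 and 3.

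**Behaviour with no effect:** partial eta squared then follows a Beta(1/2, 37/2) distribution, with mean 1/38 = 0.026 and median 0.012. The mean under no effect is larger than the value that a true 3-point difference maps to when s = 10 (0.024).

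**Precision of the adjusted difference:** half-width = t(0.975, df) × SE.
- 40 analysed (df 37): 2.29 (s = 3.57) to 6.41 (s = 10).
- 32 analysed (df 29): 2.58 to 7.23.
- For SD 10 and r = 0.5 with 40 analysed the half-width is 5.55. An observed difference of −2.5 would then have an interval from −2.5 − 5.55 = −8.05 to −2.5 + 5.55 = 3.05.

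**Effect of the threshold mismatch on responder counts:** the SD of individual change is SD × √(2(1 − r)), from 5 × √0.6 = 3.9 to 10 × √2 = 14.1. With normal changes and a mean improvement of 0 to 4 points (assumed), P(improvement ≥ 2.5) − P(improvement ≥ 3) runs from 0.014 to 0.051. Multiplied by 20, that is 0.28 to 1.03 participants per arm. This is a continuous approximation; real T-scores come from a conversion table and are discrete, so the actual shift depends on that table.

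**The case against.** The strongest reply is that partial eta squared is not asked to carry clinical meaning. Straight after naming it, the plan turns to clinical relevance with a responder comparison that has both direction and T-score units. The ANCOVA itself is sound, ordinary software can give the adjusted difference and its interval, and naming one statistic does not forbid others. On this view the point is about incomplete reporting and not about a wrong analysis. On the thresholds, a difference in Section 2 and an MID achieved by participants in Section 11.2.2 can reasonably be read as a group-level and a person-level value, and the effect on counts is small. The low end of the assumed SD range also has no support in the documents: with SD 6 to 10, partial eta squared is 0.017 to 0.084 for 2.5 points and 0.024 to 0.117 for 3 points, and the half-width is 2.75 to 6.41 with 40 analysed.

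Much of this stands. The model is valid, the responder comparison partly fills the gap, and the thresholds do not demonstrably contradict each other. But the responder comparison dichotomises the outcome, has no interval planned, and does not give the size of the mean effect. That software can give a result does not commit the team to reporting it, and the plan chose a different statistic. The narrower SD range changes the end figures and leaves the conclusion as it is.

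**Conclusion.** The concern holds and the plan should be changed. The main point is that the primary comparison has no pre-specified effect estimate in T-score points and no confidence interval, in a trial that disclaims power but whose primary objective is directional and whose benchmark is in T-score points. Under the assumed SD of 5 to 10 and r of 0 to 0.7, one reported partial eta squared can stand for T-score differences that vary by a factor of 2.8 (4.41/1.58), with the direction unknown. An interval half-width of roughly 2 to 6 points would go unstated. The gap itself is a matter of text and does not depend on these assumptions; only its illustrated size does. The unreconciled 2.5 and 3 are a minor clarification, affecting about one participant per arm at most, and would not justify the recommendation alone.

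**What to change.** 1. In Section 11.2.2, name as the main effect size the baseline-adjusted difference in 8-week T-score from the planned ANCOVA, intervention minus control, with its two-sided 95% CI, and state that a negative value favours the intervention. Keep partial eta squared as a supplement.
2. Before any 8-week data are examined, reconcile Sections 2 and 11.2.2. Either give one threshold, with its direction (a decrease), in both places, or label 2.5 and 3 by role (difference between groups, or change within a person from baseline) and use each only in that role. The documents do not settle which value is right, so the study team must state it.

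The cost is a few sentences in Section 11.2.2 and in the Section 2 endpoint table. The model, the data collected and the sample size stay as they are.

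### The MID responder comparison is planned as an unadjusted chi-squared test at about 20 per arm, with no difference in percentages, no confidence interval and no adjustment for the baseline T-score

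*Combined protocol and SAP*

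**What the plan says.** Section 11.2.2 models the 8-week score by treatment group, "with the baseline value of the outcome as a covariate". The effect measure for that model is fixed: "Effect size will be indicated by partial eta squared for the treatment group variable".

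For potential clinical relevance, the same section turns to a responder comparison: "we will use chi-squared tests to compare the percentage of participants in each treatment condition". A responder here is anyone "who achieved the Minimally Important Difference (MID) of ≥ 3 T-score points in PROMIS pain interference". The section names no covariate, no difference or ratio of percentages, and no interval for this comparison. No confidence interval is planned anywhere in section 11.

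Section 11.1 says: "This pilot study is not powered to determine the statistical significance of effects". The protocol summary gives the size, "We will recruit 40 adults from a FQHC who are age 50+ with high-impact chronic pain", and section 3.1 gives the allocation, "Participants will be allocated into the two study arms in a 1:1 ratio by block randomization with mixed block sizes". The objectives table in section 2 carries a separate benchmark for the primary endpoint: "A 2.5 point difference in T-score is considered clinically significant".

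**The concern.** A chi-squared test yields a p-value. In a trial this small, that p-value will be inconclusive for most responder differences of interest, and it does not show how large a benefit the data still allow. That range is what a pilot needs to pass on to the design of a larger trial. Partial eta squared does not fill the gap, since it is in neither T-score nor percentage units.

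The second part concerns baseline. People who start with worse pain interference are more likely to improve by 3 points whatever the treatment, through regression to the mean. The continuous analysis allows for this and the responder analysis does not. A chance baseline difference between arms would therefore carry into the responder percentages, in favour of the arm that started worse, while being removed from the main result. The two analyses could then point in different directions for no reason but the baseline draw.

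**Working it through.** **Inputs.** From the documents: 40 randomized 1:1, so 20 per arm before dropout; responder threshold 3 T-score points. The documents give no alpha, responder rates, trial-specific SD, baseline to follow-up correlation or dropout rate. Assumed here: two-sided 0.05; responder rates as shown; SD 7 to 10; correlation r 0.5 to 0.7; normal scores. The plan has no figure of its own to reproduce.

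**1. What the test would show.** Take 6/20 control and 10/20 intervention responders.

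- Pooled rate 16/40 = 0.40. z = 0.20 / √(0.40 × 0.60 × 2/20) = 0.20 / 0.155 = 1.29, so p = 0.197.
- Wilson limits are 0.299 to 0.701 for 10/20 and 0.145 to 0.519 for 6/20. Newcombe lower limit: 0.20 − √[(0.500 − 0.299)² + (0.519 − 0.300)²] = 0.20 − 0.297 = −0.10. Upper limit: 0.20 + √[(0.701 − 0.500)² + (0.300 − 0.145)²] = 0.20 + 0.253 = 0.45.
- Against 6/20, 12/20 gives p = 0.057 and 13/20 gives p = 0.027, so a 35-point difference is needed for p < 0.05.
- Exact power for true rates of 30% versus 50% is 24.5%.

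**2. Validity.** By exact enumeration at 20 per arm, the type I error of the uncorrected test is 0.039 to 0.053 for common rates of 10% to 50%. The test is sound.

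**3. Dependence on baseline.** With no treatment effect and no drift, the chance of a 3-point improvement for someone k SDs above the baseline mean is 1 − Φ[(3 − (1 − r)·k·SD) / (SD·√(1 − r²))]. At SD 8 and r = 0.5:

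- k = −1: 1 − Φ(7/6.93) = 16%
- k = +1: 1 − Φ(−1/6.93) = 56%

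**4. Effect of a chance imbalance.** One standard error of the baseline difference is SD·√(2/20) = 0.316·SD, which is 2.2 points at SD 7 and 3.2 at SD 10. The average slope of responder probability on baseline is (1 − r)·φ(3/s)/s, where s = SD·√(2(1 − r)) is the SD of change. The shift is slope × imbalance. The standard error of the unadjusted difference is √(2p(1 − p)/20), with p = 1 − Φ(3/s).

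| SD | r | s | slope | shift (points) | standard error (points) | ratio |
|---|---|---|---|---|---|---|
| 7 | 0.5 | 7.00 | 0.0260 | 5.8 | 14.9 | 0.39 |
| 7 | 0.7 | 5.42 | 0.0189 | 4.2 | 14.4 | 0.29 |
| 10 | 0.5 | 10.00 | 0.0191 | 6.0 | 15.4 | 0.39 |
| 10 | 0.7 | 7.75 | 0.0143 | 4.5 | 15.1 | 0.30 |

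**5. What adjustment buys.** In simulations at these settings with a 4-point mean effect, linear regression of the 0/1 responder variable on arm and baseline T-score cut the shift to under 1 point. It lowered the sampling SD of the difference from 0.149–0.155 to 0.142–0.149, about 3 to 7%. The power gain was about 0 to 4 percentage points with the HC3 robust standard error and 3 to 6 with HC1. Type I error stayed near 5%.

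**The case against.** The strongest reply is that this is a supporting comparison, worded as potential relevance, in a pilot that openly disclaims power. The main efficacy model is already protected against baseline imbalance. The two percentages will be reported, so a reader can subtract them. An interval of −10 to +45 is no more conclusive than p = 0.20, and the low power follows from the sample size, not from the choice of test. All of that stands, and it keeps the point modest. It does not remove it: subtraction gives the difference but not its precision, and precision is what the plan omits.

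A reader might also infer more than the documents support:

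- *That the baseline score is not used at all.* Reaching the MID can only be scored as change from baseline, so baseline is built into the responder variable. What is missing is covariate adjustment in this comparison.
- *That this is the only place where clinical relevance is addressed.* Section 2 sets a 2.5-point benchmark for the primary endpoint and includes global impression of change as the participant's own view of benefit.
- *That relevance will be decided by p < 0.05.* Section 11 states no alpha and no decision rule.
- *That the test is invalid or biased.* Its size is acceptable, and under randomization a chance baseline imbalance is noise, not bias.

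Regression at 20 per arm brings its own choice of small-sample standard error, and the gain in power is small. That is a fair cost, and it argues for keeping the unadjusted figures in view.

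**Conclusion.** The point holds as a modest improvement worth considering. A valid but uninformative test is planned where an estimate with an interval is available from the same data, and the responder comparison is handled differently from the main model with respect to baseline.

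The missing difference and interval are the stronger half. With the assumed counts, the interval shows that anything from a 10-point deficit to a 45-point benefit remains compatible with the data, which p = 0.20 does not convey. The baseline half is smaller: a one-standard-error imbalance amounts to 0.3 to 0.4 of the standard error of the difference, and the gain in precision is a few percent. These sizes rest on the assumed responder rates, SD, correlation and normal scores, and on 20 per arm with no dropout. Loss to follow-up would widen the interval.

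**What to change.** In section 11.2.2, replace the chi-squared test with the between-arm difference in the percentage improving from baseline by at least the MID, adjusted for the baseline T-score and reported with a 95% confidence interval. Linear regression of the 0/1 responder variable on arm and baseline T-score will do, with a small-sample robust standard error such as HC3 named in advance. Show the unadjusted percentages and their difference with a Newcombe interval alongside. State that the clinical-relevance conclusion rests on the estimate and interval.

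In the same edit, write improvement from baseline into the responder definition, and reconcile the 3 points in section 11.2.2 with the 2.5 points in section 2.

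The cost is a few sentences in the SAP and a few lines of code, with no new data. The downside is slightly more analysis and one extra choice of standard error to prespecify.
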